### **10.3.1 Reporting Procedures**

#### General

All adverse events will be captured on the appropriate study-specific case report forms (CRFs). All serious adverse events, regardless of causality to study drug, will be reported promptly to the Principal Investigator and/or the Study Coordinator. Participating network sites refer to appendix D for reporting instructions.

Institutional Review Board (IRB)

All adverse events/serious adverse events will be reported to the IRB per current institutional standards. If an adverse event requires modification of the study protocol and informed consent, these modifications will be provided to the IRB with the report of the adverse event.

External AgenciesExpedited Adverse Event Reporting – NCI/CTEP

Expedited reports are submitted to CTEP via the secure CTEP-AERS application accessed via the CTEP web site

(<https://eapps-ctep.nci.nih.gov/ctepaers/pages/task?rand>). Those AEs that do not require expedited reporting must be reported in routine (CDUS) study data submissions. AEs reported through CTEP-AERS must **also** be reported in routine study data submissions.

In the rare event when Internet connectivity is disrupted a 24-hour notification is to be made to NCI by telephone at: [contact] or [contact] for CIP studies or fax to [contact]. An electronic report must be submitted immediately upon re-establishment of the internet connection.

Expedited Reporting Guidelines: Phase 1 Trials Utilizing an Agent under a CTEP IND: CTEP-AERS Reporting Requirements for Adverse Events That Occur Within 30 Days of the Last Dose of the Investigational Agent.

	Grade 1	Grade 2	Grade 2	Grade 3		Grade 3		Grades 4 & 5 
	Unexpected and Expected	Unexpected	Expected	Unexpected with Hospitalization	Unexpected without Hospitalization	Expected with Hospitalization	Expected without Hospitalization	Unexpected and Expected
Unrelated Unlikely	Not Required	Not Required	Not Required	10 Calendar Days	Not Required	10 Calendar Days	Not Required	24-Hour; 5 Calendar Days
Possible Probable Definite	Not Required	10 Calendar Days	Not Required	24-Hour; 5 Calendar Days	24-Hour; 5 Calendar Days	10 Calendar Days	Not Required	24-Hour; 5 Calendar Days

 Adverse events with attribution of possible, probable, or definite that occur greater than 30 days after the last dose of treatment with an agent under a CTEP IND require reporting as follows:
 
CTEP-AERS 24-hour notification followed by complete report within 5 calendar days for:
 
 
Grade 3 unexpected events with hospitalization or prolongation of hospitalization
 
Grade 4 unexpected events
 
								

- Grade 5 expected events and unexpected events

 Although a CTEP-AERS 24-hour notification is not required for death clearly related to progressive disease, a full report is required as outlined in the table.

December 15, 2004

***Note: All deaths on study require both routine and expedited reporting regardless of causality. Attribution to treatment or other cause must be provided.***

- Expedited AE reporting timelines defined:
  - “24 hours; 5 calendar days” – The investigator must initially report the AE via CTEP-AERS within 24 hours of learning of the event followed by a complete CTEP-AERS report within 5 calendar days of the initial 24-hour report.
  - “10 calendar days” - A complete CTEP-AERS report on the AE must be submitted within 10 calendar days of the investigator learning of the event.
- Any medical event equivalent to CTCAE grade 3, 4, or 5 that precipitates hospitalization (or prolongation of existing hospitalization) must be reported regardless of attribution and designation as expected or unexpected with the exception of any events identified as protocol-specific expedited adverse event reporting exclusions.
- Any event that results in persistent or significant disabilities/incapacities, congenital anomalies, or birth defects must be reported via CTEP-AERS if the event occurs following treatment with an agent under a CTEP IND.
- Use the NCI protocol number and the protocol-specific patient ID provided during trial registration on all reports.

Phase 2 Trials Utilizing an Agent under a CTEP IND: CTEP-AERS Reporting Requirements for Adverse Events That Occur Within 30 Days of the Last Dose of the Investigational Agent

	Grade 1	Grade 2	Grade 2	Grade 3		Grade 3		Grades 4 & 5 	Grades 4 & 5 
	Unexpected and Expected	Unexpected	Expected	Unexpected with Hospitalization	Without Hospitalization	Expected with Hospitalization	without Hospitalization	Unexpected	Expected
Unrelated Unlikely	Not Required	Not Required	Not Required	10 Calendar Days	Not Required	10 Calendar Days	Not Required	10 Calendar Days	10 Calendar Days
Possible Probable Definite	Not Required	10 Calendar Days	Not Required	10 Calendar Days	10 Calendar Days	10 Calendar Days	Not Required	24-Hour; 5 Calendar Days	10 Calendar Days

 Adverse events with attribution of possible, probable, or definite that occur greater than 30 days after the last dose of treatment with an agent under a CTEP IND require reporting as follows:

CTEP-AERS 24-hour notification followed by complete report within 5 calendar days for:

- Grade 4 and Grade 5 unexpected events

CTEP-AERS 10 calendar day report:

- Grade 3 unexpected events with hospitalization or prolongation of hospitalization
- Grade 5 expected events

 Although a CTEP-AERS 24-hour notification is not required for death clearly related to progressive disease, a full report is required as outlined in the table.

December 15, 2004

**Note: All deaths on study must be reported using expedited reporting regardless of causality. Attribution to treatment or other cause should be provided.**

- Expedited AE reporting timelines defined:
  - “24 hours; 5 calendar days” – The investigator must initially report the AE via CTEP-AERS within 24 hours of learning of the event followed by a complete CTEP-AERS report within 5 calendar days of the initial 24-hour report.
  - “10 calendar days” - A complete CTEP-AERS report on the AE must be submitted within 10 calendar days of the investigator learning of the event.
- Any medical event equivalent to CTCAE grade 3, 4, or 5 that precipitates hospitalization (or prolongation of existing hospitalization) must be reported regardless of

attribution and designation as expected or unexpected with the exception of any events identified as protocol-specific expedited adverse event reporting exclusions.

- Any event that results in persistent or significant disabilities/incapacities, congenital anomalies, or birth defects must be reported via CTEP-AERS if the event occurs following treatment with an agent under a CTEP IND.
- Use the NCI protocol number and the protocol-specific patient ID provided during trial registration on all reports.

Expedited Adverse Event Reporting Exclusions – Not Applicable

### 10.3.2 Unanticipated Problems

#### Definition

An Unanticipated Problem is any unexpected event that affects the rights, safety or welfare of subjects or others that result from the research. This may involve physical, social, psychological, legal or other risks.

An event is an Unanticipated Problem when it fulfills the definition above; it must be related or possibly related to the research and it must be Serious (see section 8.2). Unanticipated is defined as the nature, severity, or frequency of the event is not consistent with the current Investigator's Brochure, protocol or alternative risk information and is not due to the progression of a disease process.

An Unanticipated Problem (UAP) is any incident, experience, or outcome that meets all of the following criteria:

1. Unexpected (in terms of nature, severity, or frequency) given:
  - (a) the research procedures that are described in the study- related documents, including study deviations, as well as issues related to compromise of patient privacy or confidentiality of data;
  - (b) the characteristics of the subject population being studied
2. Related or possibly related to participation in the research (possibly related means there is a reasonable possibility that the incident, experience, or outcome may have been caused by the procedures involved in the research)
3. Suggests that the research places subjects or others at a greater risk of harm (including physical, psychological, economic, or social harm) than was previously known or recognized and deemed **Serious**.

#### 10.3.2.1 Reporting Unanticipated Problems

The principal investigator or delegated research staff will submit an Unanticipated Problem Form to the CRS Compliance Office via [contact] or email:

**NCI Protocol #: 7870**

CRSCompliance for all unanticipated problems and adverse events that are serious and deemed related or possibly related to the research drug, biologic or intervention.

#### 10.3.2.2 Secondary AML/MDS

All secondary malignancies that occur following treatment with an agent under an NCI/IDE must be reported via CTEP-AERS. CTCAE v4.0 has three options available to describe treatment-related events:

- Leukemia secondary to on oncology chemotherapy.
- Myelodysplastic syndrome
- Treatment related secondary malignancy

If you are reporting in CTCAE v3.0, the event can be reported as: “Secondary malignancy-Other (specify)”.

### 10.4 Data and Safety Monitoring

Scheduled meetings will take place monthly and include the protocol principal investigator, study coordinators, research nurses, and, when appropriate, the collaborators, sub-investigators, and biostatistician involved with the conduct of the protocol. During these meetings the investigators will discuss matters related to: safety of protocol participants, validity and integrity of the data, enrollment rate relative to expectation, characteristics of participants, retention of participants, adherence to protocol (potential or real protocol violations), data completeness, and progress of data for secondary objectives such as surrogate markers. A review of all grade 3/4 toxicities will take place in each of the meetings as well as any delays in surgical procedure or in wound healing that may be contributed to study drug.

Quarterly reports will be sent to CTEP according to specified CTEP guidelines.

### 10.5 CTEP Multicenter Guidelines

#### 10.5.1 Responsibilities of the Principal Investigator.

- The Principal Investigator will be the single liaison with the CTEP Protocol and Information Office (PIO). The Principal Investigator is responsible for the coordination, development, submission, and approval of the protocol as well as its subsequent amendments. The protocol must not be rewritten or modified by anyone other than the Principal Investigator. There will be only one version of the protocol, and each participating institution will use that document. The Principal Investigator is responsible for assuring that all participating institutions are using the correct version of the protocol.
- The Principal Investigator is responsible for the overall conduct of the study at all participating institutions and for monitoring its progress. All reporting requirements to CTEP are the responsibility of the Principal Investigator.

- The Principal Investigator is responsible for the timely review of Adverse Events (AE) to assure safety of the patients.
- The Principal Investigator is responsible for the review of and timely submission of data for study analysis.

### **10.5.2 Responsibilities of the Coordinating Center**

- Each participating institution will have an appropriate assurance on file with the Office for Human Research Protection (OHRP), NIH. The Coordinating Center is responsible for assuring that each participating institution has an OHRP assurance and must maintain copies of IRB approvals from each participating site.
- Prior to the activation of the protocol at each participating institution, an OHRP form 310 (documentation of IRB approval) must be submitted to the CTEP PIO.
- The Coordinating Center assures that IRB approval has been obtained at the participating site prior to the first patient registration from that site.
- The Coordinating Center is responsible for the preparation of all submitted data for review by the Protocol Chair.
- The Coordinating Center maintains documentation of AE reports. The participating institution reports directly to CTEP with a copy to the Coordinating Center. The Coordinating Center will submit AE reports to the Protocol Chair for timely review.
- Audits may be accomplished in one of two ways: (1) source documents and research records for selected patients are brought from participating sites to the Coordinating Center for audit, or (2) selected patient records may be audited on-site at participating sites. If the NCI chooses to have an audit at the Coordinating Center, then the Coordinating Center is responsible for having all source documents, research records, all IRB approval documents, NCI Drug Accountability Record forms, patient registration lists, response assessments scans, x-rays, etc. available for the audit.

### **10.5.3 Patient Registration**

The coordinating Center serves as the central location for registering all patients enrolled in a multi-center trial. Refer to network appendix D for patient registering instructions.

### **10.6 Cooperative Research and Development Agreement (CRADA)/Clinical Trials Agreement (CTA)**

The agent(s), supplied by CTEP, DCTD, NCI, used in this protocol is/are provided to the NCI under a Collaborative Agreement (CRADA, CTA) between the Pharmaceutical Company(ies) [hereinafter referred to as "Collaborator(s)"] and the NCI Division of Cancer Treatment and Diagnosis. Therefore, the following obligations/guidelines, in addition to the provisions in the

**NCI Protocol #: 7870**

Intellectual Property Option to Collaborator@ contained within the terms of award, apply to the use of Agent(s) in this study:

1. Agent(s) may not be used for any purpose outside the scope of this protocol, nor can Agent(s) be transferred or licensed to any party not participating in the clinical study. Collaborator(s) data for Agent(s) are confidential and proprietary to Collaborator(s) and shall be maintained as such by the investigators. The protocol documents for studies utilizing investigational agents contain confidential information and should not be shared or distributed without the permission of the NCI. If a copy of this protocol is requested by a patient participating on the study or patient's family member, the individual should sign a confidentiality agreement. A suitable model agreement can be downloaded from <http://ctep.cancer.gov>.
2. For a clinical protocol where there is an investigational Agent used in combination with (an)other investigational Agent(s), each the subject of different collaborative agreements, the access to and use of data by each Collaborator shall be as follows (data pertaining to such combination use shall hereinafter be referred to as "Multi-Party Data".):
  - a. NCI must provide all Collaborators with prior written notice regarding the existence and nature of any agreements governing their collaboration with NIH, the design of the proposed combination protocol, and the existence of any obligations that would tend to restrict NCI's participation in the proposed combination protocol.
  - b. Each Collaborator shall agree to permit use of the Multi-Party Data from the clinical trial by any other Collaborator solely to the extent necessary to allow said other Collaborator to develop, obtain regulatory approval, or commercialize its own investigational agent.
  - c. Any Collaborator having the right to use the Multi-Party Data from these trials must agree in writing prior to the commencement of the trials that it will use the Multi-Party Data solely for development, regulatory approval, and commercialization of its own investigational agent.
3. Clinical Trial Data and Results and Raw Data developed under a Collaborative Agreement will be made available exclusively to Collaborator(s), the NCI, and the FDA, as appropriate and unless additional disclosure is required by law or court order. Additionally, all Clinical Data and Results and Raw Data will be collected, used and disclosed consistent with all applicable federal statutes and regulations for the protection of human subjects, including, if applicable, the *Standards for Privacy of Individually Identifiable Health Information* set forth in 45 C.F.R. Part 164.
4. When a Collaborator wishes to initiate a data request, the request should first be sent to the NCI, who will then notify the appropriate investigators (Group Chair for Cooperative Group studies, or PI for other studies) of Collaborator's wish to contact them.
5. Any data provided to Collaborator(s) for phase 3 studies must be in accordance with the guidelines and policies of the responsible Data Monitoring Committee (DMC), if there is a DMC for this clinical trial.

6. Any manuscripts reporting the results of this clinical trial must be provided to CTEP for immediate delivery to Collaborator(s) for advisory review and comment prior to submission for publication. Collaborator(s) will have 30 days from the date of receipt for review. Collaborator shall have the right to request that publication be delayed for up to an additional 30 days in order to ensure that Collaborator's confidential and proprietary data, in addition to Collaborator(s)'s intellectual property rights, are protected. Copies of abstracts must be provided to CTEP for forwarding to Collaborator(s) for courtesy review as soon as possible and preferably at least three (3) days prior to submission, but in any case, prior to presentation at the meeting or publication in the proceedings. Press releases and other media presentations must also be forwarded to CTEP prior to release. Copies of any manuscript, abstract, and/or press release/ media presentation should be sent to:

Regulatory Affairs Branch, CTEP, DCTD, NCI  
[name]  
Bethesda, Maryland 20892  
[contact]  
Email: [contact]

The Regulatory Affairs Branch will then distribute them to Collaborator(s). No publication, manuscript or other form of public disclosure shall contain any of Collaborator's confidential/proprietary information.

## **11. STATISTICAL CONSIDERATIONS**

### **11.1 Study Design-**

This is a phase I/II study of high dose interleukin 2 in combination with the histone deacetylase inhibitor entinostat in patients with metastatic renal cell carcinoma. The Phase I portion of the study will be used to evaluate the safety and tolerability of high dose interleukin 2 in combination with entinostat. High dose interleukin 2 (IL-2) is the standard of care for this patient population. It is hoped that a minimum effective dose of entinostat would enhance immune response with little additional toxicity. Because response rate may not fully reflect the additional immune response attributable to entinostat and because IL-2 is the standard of care, a single-stage design will be used in the Phase II portion of the study to estimate the efficacy of the drug combination. Secondary endpoints will be used to understand the effect of entinostat and IL-2 on progression free survival (PFS) and parameters measuring immune response. A sequential probability ratio test (SPRT) will be used to provide a statistical threshold for stopping the study in case there is evidence of a larger proportion of extended grade 4 toxicities than allowed.

### **11.2 Phase I**

Primary Objective:

High-dose interleukin (IL-2) is the current standard therapy for metastatic renal cell carcinoma and its toxicity in a phase III study has been reported. The primary objective of this portion of the study is to determine a recommended dose of the biologic agent, entinostat, when combined

**NCI Protocol #: 7870**

with IL-2. The IL-2 dose level is 600,000 IU/kg, every 8 hours, IV. The current recommended dose of entinostat when administered as a single agent every second week continuously is 10 mg/m^2. The entinostat study dose levels are 1, 3 and 5 mg, every 2 weeks, PO with 3 mg chosen as the starting dose for this study. A DLT will be defined as extended grade 4 toxicity (duration of one week or more) during the first 45 days of treatment with the recommended dose being the highest dose at which 0 or 1 DLTs are observed. A DLT rate of  $\leq 33\%$  will be permitted for further evaluation in the Phase II portion of the study.

The first dose level will have a minimum of 3 patients treated (unless the first 2 patients experience dose-limiting toxicity(s) (DLT) before 3rd patient is enrolled. If a DLT occurs in 1 patient treated at the starting dose level, another 3 patients will be treated at this dose level. If DLTs occur in 2 patients in the first 6 patients, patients will be treated at a lower dose level (entinostat 1 mg PO every 2 weeks, dose level 0) and DLT will be evaluated similarly. If DLT occurs in 1/6 patients, dose level 1 will be considered the recommended Phase II dose.

If no DLTs occur at the starting dose level 1, 3 or 4 patients will be treated at the next dose level (level 2) with 5 mg PO every 2 weeks (wait 45 days for DLT assessment on first 2 patients before 3rd patient is enrolled). If no DLTs occur at dose level 2, this dose level will be recommended for the phase II portion of the study. If a DLT occurs in 1 patient at dose level 2, another 3 or 4 patients will be treated at this dose level. If DLT occurs in 2/6 patients at dose level 2, dose level 1 will be the recommended for the Phase II. If a DLT occurs in 1/6 patients, dose level 2 will be considered the recommended Phase II dose.

Patients who experience prolonged grade 4 toxicity (more than one week) and recover to  $\leq$  Grade 1 (or to pretreatment baseline level toxicity) may continue treatment at the next entinostat lower level. Once the entinostat has been dose reduced, patients must remain at the reduced dose for the remainder of the study. Patients may have their dose de-escalated twice before being removed from the trial. Patients will be allowed to remain on the therapy provided that they are tolerating the treatment and do not develop progressive disease. No dose de-escalation for IL-2 will be performed.

#### Secondary Objective:

The secondary objective of this portion of the study will describe the toxicity and tolerability of the combination of IL-2 and entinostat. An exact binomial proportion with a 95% confidence interval will be given for prolonged grade 4 toxicity. The frequency and grade of toxicities will be tabulated for each dose level. Summary statistics (mean, standard deviation, frequency) will be used to record the number of doses of IL-2 administered during the first cycle of therapy and the toxicity after the scheduled 9th dose IL-2.

### 11.3 Phase II

#### Primary Objective:

Once a recommended dose has been determined in the Phase I portion of the study, the cohort will be expanded so that 36 new patients will be treated at this dose level. The primary objective of this phase is to evaluate the safety and efficacy of the combination of entinostat and IL-2. The primary endpoint is overall response rate (complete plus partial). Enrollment is expected to be

between 1 and 2 patients per month. The combination treatment will be considered unsuccessful if the response rate is 20% or less, and it will be considered active enough to pursue further if the response rate was 40% or greater. To test this hypothesis, the fixed sample size for a single-stage study with a type I error of 10% and a type II error of 10%, based on an exact binomial test, is 36. If 11 or more of the patients have a response, the hypothesis that the response rate is  $\leq 20\%$  is rejected with a target error rate of 0.10. This design has type I and type II errors of 0.09 and 0.09, respectively.

#### Secondary Objectives:

Secondary endpoints will be used to determine the effect of entinostat on progression free survival (PFS), survival, time-to tumor progression and parameters measuring immune response.

Failure rates will be used to compare the PFS, overall survival and time-to-tumor progression of metastatic RCC patients treated with high dose aldesleukin combined with entinostat to the historical failure rates of patients treated with high dose aldesleukin alone. The failure rate is estimated by dividing the number of events ( $d$ ) by the sum of the exposure time in the study

cohort:  $\lambda = d / \sum t_i$ . The 95% confidence interval is calculated as:  $\lambda \pm Z_{1-\alpha/2} \frac{\lambda}{\sqrt{d}}$ .

The historical PFS failure rate observed in the randomized trial of IL-2 reported by the Cytokine Working Group was 2.77 per person year (median PFS of 3 months). Patients eligible for this study are expected to be homogenous group with comparable prognostic characteristics. Enrollment is expected to be between 1 and 2 patients per month with an accrual period of 6 years and 12 months of follow-up. With a total of 34 events in 36 patients, the study would yield 79% power to detect a decrease in the PFS failure rate to 1.85 per person year of follow-up (an increase of 1.5 months in the median PFS compared to the historical median) at an alpha level of 0.1 (one-sided).

We do not expect that different doses of entinostat during the period off aldesleukin (maintenance) will affect the primary endpoint since objective responses have been rarely observed with single agent entinostat. We expect that the vast majority of patients will be able to tolerate the 10 mg maintenance dose if the phase II recommended dose in combination with aldesleukin is 5 mg. Should we observe discrepancies in the maintenance dose level of entinostat we will consider subgroup analysis to determine the secondary objective PFS in the different group of patients.

The toxicity of IL-2 when combined with entinostat will be further characterized following the phase II portion of this study. The exact binomial proportion for prolonged grade 4 toxicities with the 95% confidence interval will be given. Additional toxicity frequencies, proportions, and 95% CIs will be given by type and grade of toxicity.

The association between responses (e.g. response, progression free and overall survival) and baseline laboratory parameters (e.g. CD4+, CD4+/Foxp3, CD8+, Ki 67, Tumor) will be summarized graphically (boxplots, scatterplots, Kaplan-Meier curves) and numerically (means, medians). For binary outcomes such as response, logistic regression will be used to assess the significance of associations individually (univariate) and while adjusting for other variables (multivariate). The Cox proportional hazards model will be used to model the effect of these

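### The symmetric 95% interval for the PFS, OS and time-to-progression failure rates sits too low at these event counts; exact chi-square limits would cost nothing

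*Combined protocol and SAP*

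**What the plan says.** Section 11.3 (Phase II, Secondary Objectives) sets out the historical comparison announced as objective 1.3.1: "Failure rates will be used to compare the PFS, overall survival and time-to-tumor progression of metastatic RCC patients" against historical rates on high dose aldesleukin alone. "The failure rate is estimated by dividing the number of events" by total exposure time. One interval formula follows for all three endpoints: "The 95% confidence interval is calculated as" λ ± Z(1−α/2) × λ/√d, where d is the number of events.

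For PFS the section then gives a historical rate that "was 2.77 per person year (median PFS of 3 months"), an alternative of 1.85 per person-year, 34 events in 36 patients, and 79% power "at an alpha level of 0.1 (one-sided"). It names no test statistic and does not say how the 95% interval relates to that test. It gives no historical rate for overall survival or time to progression.

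Elsewhere Section 11 uses exact methods: an exact binomial test for response and exact binomial proportions for prolonged grade 4 toxicity.

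**The concern.** For a constant hazard and a few dozen events, the estimated rate is right-skewed around the true rate, and its estimated standard error is proportional to the estimate. When the estimate happens to be low, the interval is both centred low and too narrow, so its upper limit too easily falls below the truth. An interval built symmetrically on the rate scale can therefore have total coverage near 95% while splitting the 5% error unevenly.

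The split matters because the question has a direction. The reader will look at the upper limit to see whether the historical rate is excluded, and that limit carries the larger error. Overall survival uses the same formula and may have fewer events, so the problem may be larger there.

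**Working it through.** **Inputs.** From Section 11.3: the formula above, d = 34, N = 36, rates 2.77 and 1.85 per person-year, one-sided α = 0.10, 6 years of accrual and 12 months of follow-up. From Section 2.2: median overall survival of 17 months on high dose aldesleukin. Assumptions made here: constant hazards and, for the longer follow-up scenario, uniform accrual.

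**1. The plan's own figures.** ln 2/0.25 = 2.77 and ln 2/0.375 = 1.85, so medians of 3 and 4.5 months agree with the stated rates. The power reproduces if 34 is read as the events expected at the historical rate; 36 × (1 − e^(−2.77)) = 33.7 with 12 months per patient. Then E0 = 34, E1 = 34 × 1.85/2.77 = 22.7, and

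Φ[(34 − 22.7 − 1.282 × √34)/√22.7] = Φ(0.80) = 0.789.

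The exact Poisson version (reject at 26 or fewer events, true level 0.095) gives 0.791. The stated 79% stands, and it comes from a 0.10-level test that does not use the interval.

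**2. Tail errors of the stated interval.** With T the total exposure time and d fixed, λT follows a Gamma(d) distribution. The upper limit lies below the true rate when λT > d + 1.96√d; the lower limit lies above it when λT < d − 1.96√d. At d = 34 the cut-offs are 34 ± 1.96 × 5.831, that is 45.43 and 22.57:

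- P(Gamma(34) > 45.43) = 3.35%
- P(Gamma(34) < 22.57) = 1.47%
- total coverage = 100 − 3.35 − 1.47 = 95.2%

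| Events | True rate above upper limit | True rate below lower limit |
|---|---|---|
| 34 | 3.35% | 1.47% |
| 25 | 3.48% | 1.29% |
| 14 | 3.7% | 0.9% |
| Intended | 2.5% | 2.5% |

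Simulating the planned accrual and follow-up at 2.77 per person-year (mean about 35.9 events) gives 3.4% and 1.5%, so fixing d is not what drives the result.

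**3. Overall survival.** A 17-month exponential median is 0.489 per person-year. With 12 months per patient, 36 × (1 − e^(−0.489)) ≈ 14 events are expected; with 6 years of uniform accrual plus 12 months, about 29. In simulation of the 12-month case, where the event count is random, the stated interval misses about 5.5% above and 1% below, against about 3% and 2% for chi-square limits.

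**4. Effect of the replacement.** At an observed rate of 1.85 with 34 events, T = 34/1.85 = 18.38 person-years.

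- Stated formula: 1.85 × (1 ± 1.96/√34) = 1.23 to 2.47.
- Chi-square limits on 68 degrees of freedom: 47.09/36.76 to 92.69/36.76 = 1.28 to 2.52.

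**5. Log-scale limits.** λ × exp(±1.96/√d) at d = 34 misses 1.65% above and 3.61% below: the same imbalance, reversed.

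**6. Why the role of the interval should be stated.** If someone did use the 95% interval as the test, 2.77 would be excluded only at an observed rate of 2.77/1.336 = 2.07 or less. The exact one-sided 0.10 test on 34 observed events needs 2.77 × 68/83.31 = 2.26 or less. Between those values the two readings differ.

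**The case against.** **The defect is small.** At 34 events total coverage is right, the adverse tail is 3.4% instead of 2.5%, and in the example the upper limit moves by 0.05 against a comparator of 2.77. At the powered level the formula hardly matters: a one-sided 90% bound from the symmetric formula has true level 0.105 against 0.100. The endpoints are secondary, the study's go/no-go is response (11 of 36), and comparability with the historical series is a larger uncertainty. All of this stands and sets the weight of the point. It does not argue for keeping a formula that a better one replaces at no cost.

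**A stronger reading is tempting.** A reader might infer that the 95% interval is the decision rule, so that the comparison is really made at about one-sided 0.025 and contradicts the 0.10 behind the power. The documents do not support this. Section 11.3 never says the interval decides the comparison; the one-sided 0.10 level stands in the same set of secondary objectives; and the 79% reproduces from a test at that level. A 95% interval beside a 10% test is also how the primary endpoint is handled, in Sections 9.2.7 and 11.3. What remains is that the test is not named and the interval's role is not stated.

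**Conclusion.** The formula in Section 11.3 gives unequal tails, with the larger error on the limit that would support improvement over history: 3.4% against 1.5% at 34 events, with total coverage about 95.2%. For PFS the effect is modest. It is larger where events are fewer; overall survival may have about 14 to 29 events, a range that rests on an assumed exponential 17-month median and on how long patients are followed. Time to progression shares the formula, but the documents give no basis for its event count. All tail figures assume a constant hazard, as the plan's estimator does. No contradiction between the interval and the powered test is established, and the 79% power is not in question. This is a minor point and a free improvement.

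**What to change.** In Section 11.3, replace the interval for all three failure rates with the exact limits

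χ²(0.025, 2d)/(2 × total time) to χ²(0.975, 2d)/(2 × total time).

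These have equal 2.5% tails for a fixed event count and are close to that otherwise. Do not use log-scale limits.

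Add one sentence saying that the 95% interval is descriptive and that PFS is compared with 2.77 per person-year by the planned one-sided 0.10 test, naming the statistic. One choice is to require the one-sided 90% upper bound from the same distribution, χ²(0.90, 2d)/(2 × total time), to be below 2.77. If that form is chosen, restate the power for it: treating 34 as observed events gives about 0.86, whereas the 79% corresponds to 34 expected events.

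The cost is one formula and one or two sentences, with no new patients, visits or data.
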